TITLE OF EXPERIMENTAL STUDY:	Experimental fMRI study on the comparison of the brain function effects of a single dose of Guanfacine and Lisdexamfetamine relative to placebo in children and adolescents with ADHD.
Protocol Short Title/Acronym:	AGUALIS
Study Type:	Basic Science Study
Sponsor Name:	King's College London
Chief Investigator:	[name]
UKCRN Number:	
REC Number:	18/LO/0472

Medical Condition or Disease Under Investigation:	Attention Deficit Hyperactivity Disorder (ADHD)
Purpose of Experimental Study:	To compare single dose effects of Guanfacine extended release (GXR) and Lisdexamfetamine (LDX) relative to placebo and compared to controls on ADHD fMRI brain function during typically compromised cognitive tasks that are modulated by these drugs (motor inhibition, working memory, and sustained attention).
Primary Objective:	To investigate the common and drug-specific effects of single-dose GXR and LDX, compared to placebo on brain function in ADHD using fMRI.
Secondary Objective(s):	To assess the effects of the two drugs on performance on the tasks.
Study Design:	Cross-sectional, Case-control, Crossover, Placebo Controlled, Randomised, Single-dose and Single-site study
Endpoints:	
 1) Brain activation as measured by blood-oxygen-level-dependent (BOLD) response as obtained by functional magnetic resonance imaging for each of the 3 tasks and the resting state. 2) Dependent variables extracted from performance on tasks.
Sample Size:	20 ADHD adolescents, 8-20 years 20 healthy controls, 8-20 years
Summary of Eligibility Criteria:	
ADHD patients:
 
Meeting clinical diagnosis for Attention-Deficit Hyperactivity Disorder (ADHD); age range 8-20 years; medication-naïve or non-medicated in the 3 months; no comorbid conditions other than autism, phobias, eating disorders, oppositional defiant and conduct disorder or mild anxiety and depression; IQ > 70; heart rate > 65 beats/minute; systolic blood pressure > 90 mm Hg, diastolic blood pressure < 90 mm Hg.
 
Healthy controls:
 
No clinical diagnosis of ADHD or any other major psychiatric disorder; age range 8-20 years; psychoactive medication-free; no mental health conditions; IQ > 70.

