7.1 Study Objectives

Aim of the study

The aim of this study is to understand the mechanism of action of two recently licensed drugs for ADHD on brain function and cognition. We will compare the brain activation changes elicited by Guanfacine extended release (GXR; a non-stimulant drug) with the brain activation changes elicited by Lisdexamfetamine (LDX; a stimulant drug) and by placebo in 20 currently non-medicated patients with ADHD using functional Magnetic Resonance Imaging (fMRI). Additionally, we will test 20 unmedicated healthy controls to test for potential normalisation of the two drugs on ADHD cognition and brain function. For this purpose, we intend to scan participants during their performance of tasks of attention, working memory, and inhibition, which we know from previous studies to elicit abnormal brain activation patterns in ADHD patients (Rubia et al., 2005; Smith et al., 2006). Additionally, prior to each scanning session participants will complete a battery of neurocognitive tasks, which were previously shown to be impaired in ADHD (Rubia et al., 2007). ADHD participants

performance on the neurocognitive tasks will be compared across sessions and to the performance of healthy controls.

Objectives of the Study

The proposal is for a suitably powered experimental randomised placebo-controlled double-blind study to test the mechanism of LDX and GXR compared to placebo in ADHD children.

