13.1 Sample Size

For fMRI comparisons, a minimum N of 20 has been recommended (Thirion et al., 2007). Based on a previous fMRI comparison using whole brain analysis of acute effects of the ATX and MPH on the fMRI brain function in the same working memory task as proposed in this study, we calculated that for a power of 80% we would need an N of 15 subjects for a $p < 0.05$ and N of 20 for a $p < 0.01$ (Cubillo et al., 2013). A sample size of 20 is proposed to account for the fact that the novel contrast of GXR and LDX may potentially have a smaller effect size than the previous comparisons of MPH and ATX. Therefore, to obtain 20 complete datasets 50 patients or more will be screened. This is done to ensure enough participants meet the recruitment criteria and to account for potential dropouts.

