13.3 Analysis

Analyses of brain activation for the fMRI data will be conducted using SPM (www.fil.ion.ucl.ac.uk/spm) and FSL (www.fsl.fmrib.ox.ac.uk). All performance data will be analysed using SPSS and R. The hypotheses relating activation changes within patients after the acute drug administration will be tested using repeated measures ANOVAs with each of the 3 drug conditions as repeated measures (placebo, GXR, LDX).

Comparison between healthy controls and ADHD patients under placebo and under the two drugs will be conducted by 3 ANOVAs to test for brain abnormalities in ADHD relative to controls at baseline and to test for potential normalisation of the 2 drugs on brain activation.

14. Study Steering Committee

Supervisors will oversee the study.

15. Data Monitoring Committee

As this is an experimental study and not a clinical trial we will not have an external data monitoring committee. The supervisors of the study will form a data monitoring committee and assess the study progress and all other aspects of the study. They will meet once every 6 months.

16. Direct Access to Source Data and Documents

Only the research team and named collaborators will have access to the data.

17. Ethics & Regulatory Approvals

This protocol and related documents will be submitted for review to an NHS Research Ethics Committee (REC).

18. Quality Assurance

Monitoring of this study will be to ensure compliance with Good Clinical Practice and scientific integrity will be managed by the study team.

19. Data Handling

The supervisor will act as custodian for the study data. The following guidelines will be strictly adhered to:

- Patient data will be anonymised.
- All anonymised data will be stored on a password protected computer.
- All study data will be stored in line with the Data Protection Act.
- All study data will be archived in line with Sponsor requirements.

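### Section 13.3 neither defines normalisation nor ties its three case-control ANOVAs to the within-patient drug-v-placebo contrast, so a drug with no effect could be called normalising

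*Combined protocol and SAP*

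**What the plan says.** Section 13.3 plans two analyses of brain activation in consecutive paragraphs.

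- Within patients: "The hypotheses relating activation changes within patients after the acute drug administration will be tested using repeated measures ANOVAs", with placebo, GXR and LDX as the three repeated levels.
- Against controls: "Comparison between healthy controls and ADHD patients under placebo and under the two drugs will be conducted by 3 ANOVAs". These have two purposes: "to test for brain abnormalities in ADHD relative to controls at baseline", and "to test for potential normalisation of the 2 drugs on brain activation".

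Section 7.1 gives the reason for recruiting controls: "we will test 20 unmedicated healthy controls to test for potential normalisation of the two drugs on ADHD cognition and brain function". Controls are scanned once, without drug (section 8.1), so the same control data enter every comparison.

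The primary objective in the synopsis is "To investigate the common and drug-specific effects of single-dose GXR and LDX, compared to placebo on brain function in ADHD using fMRI". Section 13.1 bases the sample size on the within-patient drug comparison. It gives no power for the comparison with controls. No section says what result would count as normalisation.

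**The concern.** Normalisation is a statement about change: patients differ from controls without the drug, and the drug moves them toward controls. An ANOVA of controls against patients in one condition cannot show change. Three of them side by side show which comparisons reach significance, and a difference between a significant and a non-significant result is not itself a test of the difference.

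Placebo v control is the right test for its other purpose, abnormality at baseline. The gap concerns normalisation only. As 13.3 stands, a region could be reported as normalised because the drug-v-control test happened to miss significance, although the patients' own drug-minus-placebo change was negligible. What is at stake is the aim for which the 20 controls are recruited.

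**Working it through.** **Plan's own figure.** None exists for the case-control or normalisation analysis. The pairs in 13.1 (15 patients at 0.05, 20 at 0.01, 80% power) concern the drug comparison. They come without an effect size, so they cannot be reproduced. This point does not depend on them.

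**What each analysis contains.** Taking one ANOVA per patient condition:

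| Analysis in 13.3 | Compares | Drug v placebo inside? |
|---|---|---|
| Repeated-measures ANOVA | placebo, GXR, LDX within patients | yes, as a contrast of the model |
| ANOVA 1 | controls v patients on placebo | no |
| ANOVA 2 | controls v patients on GXR | no |
| ANOVA 3 | controls v patients on LDX | no |

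**Inputs.** From the documents: 20 patients with three conditions each, and 20 controls with one scan. Assumed: true deficit D of 0.6, 0.8, 0.9 or 1.2 SD; within-patient correlation r of 0.3, 0.5 or 0.7; a single region; two-sided 0.05.

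**Precision against controls.** The 95% half-width is t(38, 0.975) × sqrt(2/20) = 2.024 × 0.316 = 0.64 SD. A non-significant drug-v-control result is therefore compatible with a sizeable remaining gap.

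**Model.** Controls ~ N(0, 1). Patient value = -D + subject effect (variance r) + residual (variance 1 - r). The drug is inert. The drug-minus-placebo contrast uses the pooled residual of the three-condition model (38 df). There were 200,000 simulated trials per setting.

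- *Pattern*: placebo v control significant in the deficit direction, and drug v control not significant.
- *Linked rule*: placebo v control significant, and drug-minus-placebo significant toward controls.

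**Inert drug, % of trials (r = 0.3 / 0.5 / 0.7)**

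| D | Placebo deficit significant | Pattern, all trials | Pattern, given significant deficit | Linked rule, given significant deficit |
|---|---|---|---|---|
| 0.6 | 46 | 13.9 / 11.5 / 8.9 | 30.4 / 25.2 / 19.4 | 4.5 / 4.2 / 3.9 |
| 0.8 | 69 | 12.1 / 10.3 / 7.8 | 17.4 / 14.9 / 11.3 | 3.5 / 3.3 / 3.2 |
| 0.9 | 79 | 9.7 / 8.2 / 6.4 | 12.3 / 10.4 / 8.1 | 3.1 / 3.0 / 2.9 |
| 1.2 | 96 | 2.8 / 2.4 / 1.8 | 2.9 / 2.5 / 1.9 | 2.6 / 2.6 / 2.6 |

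At 0.01, the other level in 13.1, the pattern given a significant deficit rises to 16-46% at 0.6-0.9 SD and 6-9% at 1.2 SD. A stricter threshold makes it easier not to differ from controls.

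**Drug that removes half the deficit** (D 0.6-0.9, given a significant placebo deficit)

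| Threshold | Pattern | Linked rule |
|---|---|---|
| 0.05 | 64-72% | about 30-75% |
| 0.01 | 80-84% | about 15-54% |

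**The case against.** The strongest reply is that the test of change is already planned. The repeated-measures ANOVA covers placebo, GXR and LDX, the drug-minus-placebo contrast can be taken from it, and the team may well read both analyses together. This stands in part. A reader might infer that the plan has no drug-v-placebo test, or that it commits to treating non-significance against controls as normalisation. The documents support neither inference. What is missing is a definition and a sentence joining the two analyses. Without them, the choice of how to read the results could be made after seeing them.

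Second, the three ANOVAs might be one per task, each holding controls and the patient conditions, and such a model could yield drug v placebo. This is possible. But the sentence itself lists three conditions, and section 7.1.1 has three tasks plus a resting-state scan, so one per condition is the more natural reading. Under either, normalisation is undefined and no link is stated.

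Third, the error rates belong to a reading rule that the plan does not state, and they rest on assumed inputs. This stands. They are also single-region t-test rates. Section 13.3 names SPM and FSL, and 13.1 draws on a whole-brain analysis, so the rates do not carry over directly to corrected maps. At 1.2 SD and 0.05 the problem almost disappears, and the linked rule (2.6%) is no better than the pattern (1.9-2.9%).

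**Conclusion.** The point holds as a gap in definition and linkage. Confidence is moderate, because the content of each ANOVA has to be inferred. If the three ANOVAs are read alone, an inert drug looks normalising in about 6-14% of trials at assumed deficits of 0.6-0.9 SD (8-30% given a significant placebo deficit), and in 2-3% at 1.2 SD. All of this assumes r of 0.3-0.7, one region, 20 v 20 and two-sided 0.05. The documents give no deficit size or correlation, so these figures show that the risk can matter; they are not a forecast for this study.

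A reader might go further and conclude that the main drug findings are unsound. They are not affected: the primary drug-v-placebo comparison, and what 13.1 calls "the novel contrast of GXR and LDX may potentially have a smaller effect size" (GXR against LDX), both rest on the within-patient model. This is a cheap improvement.

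**What to change.** In 13.3, before the unblinding described in 13.2, state that:

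1. Evidence of normalisation, for a brain region or a performance measure (section 7.1 covers cognition as well as brain function), requires both (i) that ADHD on placebo differs from controls and (ii) that the drug-minus-placebo contrast from the three-condition repeated-measures model is significant toward the control mean.
2. A result meeting (i) and (ii) is called a *shift toward controls*.
3. The remaining drug-v-control difference is reported as an estimate with its 95% confidence interval (about ±0.64 SD at 20 v 20). A non-significant drug-v-control test is not used as evidence of normalisation or of equality with controls.
4. The three case-control ANOVAs are one per patient condition, or one per task, whichever is meant.

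The cost is a few sentences, using models already planned, with no extra participants, scans or measures. The downside is generally fewer declarations. As the half-removal table shows, the loss is greatest at low within-patient correlation and at the 0.01 level.

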Intervention (Description, frequency, details of delivery)	
Each ADHD patient will be scanned 3 times, under either LDX, GXR, or placebo, in randomised order (visits 1, 2, 3). Each patient will receive one single clinical oral dose of GXR, LDX, and placebo and undergo a fMRI scan 4.5 hours after ingestion. Then they will receive nothing for a week and then be scanned again one week later on the single dose of the other conditions (placebo or drug) (visits 1, 2 and 3).
 
Healthy controls will be tested once, unmedicated.

Comparator Intervention:	Not applicable
Maximum Duration of the Study for a Subject:	3 weeks

Version and Date of Final Protocol:	Version 5 27/03/2019
Version and Date of Protocol Amendments:	

3. Revision History

Document ID - (Document Title) revision X.Y	Description of changes from previous revision	Effective Date

4. Glossary of terms (Optional)

ADHD = Attention Deficit Hyperactivity Disorder
 fMRI= functional Magnetic Resonance Imaging
 IoPPN = Institute of Psychiatry, Psychology & Neuroscience
 KCL = King's College London
 LDX = Lisdexamfetamine
 GXR = Guanfacine Extended Release

5. Protocol Contents

1.	PROTOCOL FULL TITLE	1
2.	STUDY SYNOPSIS	3
3.	REVISION HISTORY	5
4.	GLOSSARY OF TERMS (OPTIONAL)	5
5.	PROTOCOL CONTENTS	5
6.	BACKGROUND & RATIONALE	7
7.	STUDY OBJECTIVES AND DESIGN	7
7.1	STUDY OBJECTIVES.....	7
7.1.1	Primary endpoints.....	8
7.1.2	Secondary endpoints.....	8
7.2	STUDY DESIGN	8
7.3	STUDY FLOWCHART	8
8.	STUDY DESIGN	11
8.1	STUDY DETAILS	11
8.2	FREQUENCY AND DURATION OF INTERVENTION	12
8.3	SUBJECT COMPLIANCE	12
8.4	STUDY ADHERENCE	12
8.5	CONCOMITANT MEDICATION.....	12
9.	RESEARCH ENVIRONMENT	12
10.	SELECTION AND WITHDRAWAL OF SUBJECTS	13
10.1	INCLUSION CRITERIA.....	13

10.2	EXCLUSION CRITERIA.....	13
10.3	SELECTION OF PARTICIPANTS.....	14
10.4	WITHDRAWAL OF SUBJECTS	14
10.5	EXPECTED DURATION OF STUDY.	15
11.	STUDY PROCEDURES	15
12.	ASSESSMENT OF SAFETY.....	17
12.1	SPECIFICATION, TIMING AND RECORDING OF SAFETY PARAMETERS.	17
12.2	PROCEDURES FOR RECORDING AND REPORTING ADVERSE EVENTS.....	18
12.3	STOPPING RULES	19
13.	STATISTICS.....	19
13.1	SAMPLE SIZE.....	19
13.2	RANDOMISATION.....	19
13.3	ANALYSIS	19
14.	STUDY STEERING COMMITTEE	20
15.	DATA MONITORING COMMITTEE.....	20
16.	DIRECT ACCESS TO SOURCE DATA AND DOCUMENTS	20
17.	ETHICS & REGULATORY APPROVALS	20
18.	QUALITY ASSURANCE	20
19.	DATA HANDLING.....	20
20.	DATA MANAGEMENT	20
21.	PUBLICATION POLICY.....	21
22.	INSURANCE/INDEMNITY	21

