8.1 Study Details

There will be two groups. The first group will comprise 20 ADHD patients between 8 and 20 years who will participate in the double-blind, randomised, active drug condition, within-group, placebo-controlled experimental fMRI study. The second group will consist of 20 healthy young people between 8 and 20 years old, who will act as a control group and be scanned only once under no drug. Each ADHD participant will be assessed in baseline measures during the pre-assessment. Then the ADHD patient will be scanned 3 times under each of these 3 drug conditions: GXR, LDX, and placebo. We will compare the patient groups under the acute dose of LDX and GXR with placebo in a randomised, within-group, placebo-controlled design. Every patient will receive a single typical clinical weight-adjusted dose of GXR (0.05mg/kg, being rounded to the closest dose of 1mg, 2mg, or a maximum of 3mg GXR), LDX (30mg for participants under 30kg, 50mg for participants over 30kg body weight) and placebo (10mg Vit C) in one of the scans, in a randomised order. Advice regarding drug dosage has been specifically obtained from an experienced child psychiatrist with expertise in paediatric psychopharmacology. For fMRI studies of single dose effects, it is common practice to use the standard typical clinical target dose that is given to patients after a period of titration rather than the initial dose that would be given clinically on the first day in continuous clinical drug administration where patients are titrated up to the optimal dose. This is to test for the brain effects of a typical dose of the medication under investigation in the patient population. This was also done in our previous fMRI studies where we tested the single dose effects of a standard clinical dose of Methylphenidate (0.03mg/kg) and Atomoxetine (1mg/kg) (Cubillo et al., 2012).

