It is generally agreed that for Guanfacine to show clinical effects, it should be administered continuously for approximately 6 weeks. In the case of a single dose study this is a clear limitation. Nonetheless, while behavioural effects might need long term administration to appear, it has been shown in previous fMRI studies that brain function changes will be apparent after a single dose. This is based also on similar observations in studies investigating the related drug Atomoxetine, which is also a noradrenalin agonist. Atomoxetine is also a non-stimulant medication for ADHD that shows behavioural effects after several weeks but we have shown brain function effects after one single dose in ADHD patients (Cubillo et al., 2013; Smith et al., 2013).

ADHD patients will be scanned 4.5 hours after drug administration (where drugs have shown to have maximum plasma concentration). They will be scanned 3 times, one week apart, under each drug condition (LDX, GXR, placebo). Scanning session duration: 60 min.

Healthy controls will be scanned once, under no drug condition, and complete the same protocol as ADHD patients.

Each participant will receive £20 for the pre-assessment visit and £50 for each scanning session to reimburse them for their time (i.e. £170 in total for ADHD patients and £70 for healthy controls). We will also reimburse any travel expenses and can arrange taxis or other travel if required. After each visit participants will receive a token showing the amount that he or she will be paid for the session (i.e. £20 or £50). Payments will be given at the end of the patient's participation in the study, i.e. they will exchange the tokens they collected for money.

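### As written, the three patient-v-control ANOVAs carry the patients' average session effect: control scans are all first scans, while about 13 of 20 patient scans per condition are repeats

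*Combined protocol and SAP*

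**What the plan says.** On the patient-v-control comparison, section 13.3 says: "Comparison between healthy controls and ADHD patients under placebo and under the two drugs will be conducted by 3 ANOVAs". The placebo contrast is meant to show abnormality at baseline; the two drug contrasts are meant "to test for potential normalisation of the 2 drugs on brain activation". No session, visit or order term is named, nor any restriction to first scans.

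On the controls, the synopsis says "Healthy controls will be tested once, unmedicated", and section 8.1 describes a group "who will act as a control group and be scanned only once under no drug". Patients are scanned three times at weekly intervals, once per condition. Section 13.2 randomises the order of the three conditions with the aim of controlling order effects, and names no balancing scheme. Section 11 gives both groups mock-scanner familiarisation and task training at pre-assessment.

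Section 7.1 also promises that patients' performance on the neurocognitive battery will be compared with that of controls. For performance data section 13.3 names only software: "All performance data will be analysed using SPSS and R".

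The primary objective in the synopsis is the within-patient one: "To investigate the common and drug-specific effects of single-dose GXR and LDX, compared to placebo on brain function in ADHD using fMRI".

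**The concern.** A second or third scan may differ from a first one through practice, familiarity, lower anxiety or boredom. Randomising drug order spreads such effects evenly over the three conditions within patients. It cannot spread them between patients and controls, because controls have no second or third scan.

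A two-group ANOVA without a session term attributes any such difference to group. In the placebo contrast it would be read as part of the ADHD abnormality, or would hide part of it. In the drug contrasts it would move the distance to controls on which the normalisation reading depends. Testing for normalisation is the stated reason for including controls (section 7.1). The same imbalance applies to task performance in the scanner and to the neurocognitive battery, which patients complete before each scan.

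**Working it through.** **Plan's own figure.** The documents give no session effect and no count of first or repeat scans per ANOVA, so there is nothing to reproduce. The sizes below are assumptions.

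**Inputs from the documents.** 20 patients with three scans each; 20 controls with one scan each (section 8.1); randomised order (13.2); three two-group comparisons (13.3).

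**1. Scan counts.**
- Repeat scans among controls: 0 of 20.
- Expected repeats among patients, per condition: 20 × 2/3 = 13.3.
- Near-balanced orders: six orders × 3 = 18 patients, plus 2 patients on two different further orders. Each condition is then first in 6, 7 or 8 patients, giving 12 to 14 repeats.
- Simple randomisation, binomial(20, 2/3): 95% range 9 to 17 repeats.

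**2. What each contrast estimates.** Let s2 and s3 be the effects of sessions 2 and 3 relative to session 1. With equal thirds of scans per session, a group-only contrast has expectation: group difference + (s2 + s3)/3.

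**3. Size.** Set total variance to 1, so the within-patient SD is √(1 − ICC). With session effects in within-patient SD, bias = (s2 + s3)/3 × √(1 − ICC). The standard error is √(2/20) = 0.316. Type I error comes from a noncentral t with 38 df and noncentrality bias/0.316, for one two-sided 5% test.

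| Assumed effects, sessions 1, 2, 3 | Bias in SD, ICC 0.3 / 0.5 / 0.7 | Type I error |
|---|---|---|
| 0, 0, 0 | 0 | 5% |
| 0, 0.1, 0.2 | 0.084 / 0.071 / 0.055 | 5.3 to 5.8% |
| 0, 0.3, 0.5 | 0.223 / 0.189 / 0.146 | 7.4 to 10.6% |
| 0, 0.5, 0.8 | 0.363 / 0.306 / 0.237 | 11.3 to 20.1% |

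Example, last row at ICC 0.3: (0.5 + 0.8)/3 = 0.433; 0.433 × √0.7 = 0.363. Simulating that row over every near-balanced split of scans (7/7/6 and 8/6/6 types) gives about 10 to 22%.

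**4. Effect on the normalisation reading.** Assume a true 0.9 SD deficit, no drug effect, and session effects (0, 0.5, 0.8) moving patients towards controls. Score false normalisation as abnormal under placebo and not abnormal under the drug. In simulation (40,000 runs, near-balanced orders) the rate goes from 9.7 / 8.3 / 6.3% without session effects to 13.4 / 11.4 / 9.0% with them (ICC 0.3 / 0.5 / 0.7). Allowing for simulation error, the rise is about 2 to 4 percentage points. If a significant drug-v-placebo gain is also required, the rate is about 1% either way.

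**5. Cost of adjusting.** Ratios are to the unadjusted 0.316.
- One model on all 60 + 20 = 80 scans, contrast at session 1, near-balanced orders: 1.091 to 1.122 (ICC 0.3), 1.066 to 1.089 (0.5), 1.040 to 1.054 (0.7).
- First scans only, √(1/n + 1/20)/√(2/20): n = 8 gives 1.323, n = 7 gives 1.389, n = 6 gives 1.472.
- A session term added to each separate ANOVA gives the same ratios as first scans only, because its contrast then rests on the first-scan patients.
- Simulated with (0, 0.5, 0.8), the joint model has mean bias below 0.01 SD and Type I error of 4.5 to 4.8%. Type I error is 3.7 to 3.9% if control variance is half that of patients, and 5.4 to 5.8% if it is double.

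**The case against.** **Order is already controlled, and both groups are trained beforehand.** Order control in section 13.2 equalises sessions between conditions within patients, which protects the primary objective. It does nothing for the comparison with once-scanned controls. Training may shrink a session effect, but it precedes everyone's first scan; only patients then go on to complete further full sessions.

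**Section 13.3 is a short outline, so silence does not exclude a covariate.** True, but the obvious addition, a session term in each of the three ANOVAs, is the inefficient one (standard error 32 to 47% larger). The form of the model needs to be stated.

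**Session effects may be absent or small.** This stands. The documents give neither size nor direction, the smallest non-zero scenario above is negligible, and single-test rates do not transfer directly to corrected whole-brain maps.

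**The normalisation conclusion is fairly robust.** This also stands. A reader might infer that session effects would often make an inactive drug look normalising, because a drug-v-control contrast taken alone loses significance more often when patients drift towards controls. Section 13.3 plans that contrast alongside the placebo one, which drifts by about the same amount, so the joint reading changes little. A drift away from controls would act in the opposite direction.

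**Conclusion.** The concern holds for the analysis as written: each patient-v-control contrast includes the patients' average session effect. What is mainly at risk is the size of the placebo-v-control difference; the two drug contrasts move with it by about the same amount when order is balanced. Under the assumed scenarios the bias is 0.05 to 0.36 SD. It is zero if there are no session effects.

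Two stronger readings are not supported. A reader might infer that session and group cannot be separated in this design. They can: 6 to 8 patients per condition have first scans under near-balanced orders, and every patient contributes all three sessions, so a model with session in it estimates both. A reader might also infer that the primary objective is compromised. The within-patient drug comparisons are not biased by this when order is balanced.

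The change should be made, because it is cheap and no new data are needed. Confidence in the practical size is only moderate, since every session effect used here is assumed.

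**What to change.** Replace the three separate ANOVAs with one model on all 80 scans. Use condition (control, placebo, GXR, LDX) and session (1, 2, 3) as fixed effects, with a random participant effect or an equivalent within-participant covariance. Report each patient-v-control contrast at session 1. Use the same model for in-scanner task performance and for the neurocognitive battery.

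State the assumptions: session effects additive across conditions; no carryover (section 8.2 sets 7-day intervals against calculated washouts of 4.6 and 2.4 days); and a variance common to patients and controls.

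Add a first-scan-only comparison (6 to 8 patients per condition against 20 controls) as a consistency check only. If the model cannot be fitted voxelwise, report the planned ANOVAs with the session mix of each condition and state this limitation.

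Cost: standard errors about 4 to 12% larger under near-balanced orders, and some extra modelling work. Visit number is known for every scan. If session effects are absent, nothing is gained.
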